Our goal is to identify effective, accessible, and sustainable means for improving long-term lasting weight loss, using scalable health-promoting devices in rural obese adults. This proposal aims to conduct a study of remote health monitoring using *Amulet*²¹, a Dartmouth Computer Science developed mobile health (mHealth) device, incorporated into usual health coach visits and delivered in patients' homes using video-conferencing. *Amulet* provides an adaptable platform for behavioral change; unlike commercial devices, it uses an open source programming model capable of testing an array of other strategies and non-proprietary devices²¹. We previously described the challenges in delivering obesity care^{22,23} and promises of virtual modalities in overcoming geographic barriers to care²⁴. However, use of technology in isolation, without human interactions, is unlikely to lead to success²⁵. Hence, we propose an eHealth-delivered health coaching obesity intervention that delivers IBT by trained health coaches using telehealth and *Amulet* to enhance behavioral change. Our rationale is to pilot the intervention with 30 Dartmouth-Hitchcock (D-H) Weight & Wellness Center patients to determine its potential effectiveness on weight loss, physical function, self-reported health, and care pathways in a specialty obesity clinic. If effective, the program will enhance in-home care and be disseminated to remote, low resource areas to rural obese adults lacking access to care. We will address the following Specific Aims:

Aim 1: Evaluate the feasibility and acceptability of an eHealth-delivered (remote monitoring and video-conferencing) health coaching obesity intervention in a rural, academic, specialty obesity clinic.

H1: An eHealth-delivered health coaching obesity intervention using video-conferencing and remote monitoring is: a) feasible (>80% of subjects will enroll; >80% of enrollees will complete the intervention); and b) acceptable in rural adults seeking treatment for obesity (using semi-structured interviews and Yip's Telemedicine survey).

Aim 2: Assess the potential effectiveness of an eHealth-delivered health coaching obesity intervention in improving weight, physical function and self-reported health in adults with obesity.

H2: Measures of improved weight (>5% loss), physical function (6-minute walk) & self-reported health (patient-reported outcome measurement system-PROMIS) will allow reliable estimates for designing an evaluative trial.

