e) **Remote Monitoring:** The *Amulet* is an mHealth wrist-worn device with remote sensing and self-monitoring capabilities, functioning independently of a smartphone (battery life lasts >9 days). A 9-axis gyroscope, accelerometer, magnetometer and sensor captures motion, activity type, exercise, and speed data. As part of [name] K23, *Amulet* applications were developed to measure steps, strength, and activity (sedentary, walking, running). Two-way data transfer occurs via a micro-SD card, or low-energy Bluetooth 4.0 to a secure cloud-based repository that is accessible to the team. Predetermined one-line automated scripts (if goals are not met), prompts, and asynchronous messaging can be sent by staff. Programmable reminders (blinking lights, text, haptic buzzer) and audio-visual feedback allow the *Amulet* to celebrate goal attainment.

Outcomes Measures: These were chosen based on their validity, brevity and presence within the HER:

Table 1: Study Variables and Objective Outcome Measures

Aim 1: Feasibility and acceptability of an eHealth-delivered health coaching obesity intervention						Timepoint			
Domain	Outcome/Co-Variate	Instrument	Adm	Length	Source	0	1	2	3
Feasibility	Recruitment/Retention	Eligibility, enrollment, dropout data	RA	---	Study Log	✓	✓	✓	✓
	Engagement/Assessments	>80% attend + complete sessions	RA	---	Study Log	✓	✓	✓	✓
Acceptability	Satisfaction of Intervention	Semi-structured interview	RA	30 min	Participant			✓	
	Patient Satisfaction	Yip Telemedicine questionnaire ⁶²	Self	15 item	Participant			✓	
Aim 2: Potential effectiveness in improving weight, physical function and self-reported health						Timepoint			
Domain	Outcome/Co-Variate	Instrument	Adm	Length	Source	0	1	2	3
Participant Level Outcomes	Anthropometry	Weight/body mass index	CS	---	Participant	✓	✓	✓	✓
	Physical function	6 minute walk test (6MWT) ⁶³	CS	6 min	Participant	✓			✓
	Diet/Exercise Measures	REAP-S ⁶⁴ /IPAQ ⁶⁵	Self	16/7 items	Participant	✓			✓
	Subjective Health	PROMIS general health 10 ⁶⁶	Self	10 items	Participant	✓			✓
	Readiness to Change	URICA ⁶⁷	Self	12 item	Participant	✓	✓	✓	✓
Aim 3a: Ascertain the extent to which the intervention works on implementation outcomes						Timepoint			
Domain	Outcome/Co-Variate	Instrument	Adm	Length	Source	0	1	2	3
Adoption	Workflow adoption	Qualitative Interviews	RA	30 min	Staff				✓
	Staff adoption	Evidence-based practice adoption ⁶⁸	RA	12 item	Staff				✓

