Implementation	Organizational Change	General Organizational Inventory ⁶⁹	RA	12 item	Staff				✓
Compatibility	Patient Perception of Value	Willingness to Pay ⁷⁰	Self	2 item	Participant	✓			✓

ADM- Administration; CS – clinical staff; IPAQ – International Physical Activity Questionnaire; PROMIS: Patient Reported Outcome Measures Information Systems; RA: research assistant; REAP-S: Rapid Eating Assessment for Participants – Shortened Version; 6MWT: 6-minute walk test; URICA: University of Rhode Island Change Assessment: Short Form for Physical Health Behavior State.

Aim 1: Evaluate the feasibility and acceptability of an eHealth-delivered (remote monitoring and video-conferencing) health coaching obesity intervention in a rural, academic, specialty obesity clinic.

Feasibility: The following rates will be computed: screened for inclusion ($\# \text{ screened} \div \# \text{ potentially eligible}$); eligibility [$\# \text{ screen positive} \div \# \text{ screened for inclusion}$]; enrollment [$\# \text{ enrolled} \div (\# \text{ screen positive} \& \text{ eligible})$]; completion ($\# \text{ completing sessions} \div \# \text{ enrolled}$); assessment ($\# \text{ completing all assessments} \div \# \text{ enrolled}$). We will assess entry criteria (reasons for dropout/non-adherence) and time to collect data. Enrollment success will be defined as 30 patients. Adequate retention is defined as a dropout rate of <20%. Completion of >80% of post-study measures will be defined as adequate. Attending >80% of sessions will be considered acceptable. Staff will track equipment, software or technical issues (malfunctions, data loss, hardware) in a journal.

Acceptability: Qualitative interviews will ensure the appropriateness of the pilot and its strengths/weaknesses. The RA will conduct, record, and transcribe each 30min interview. Field notes, questions, and themes outlining the content/context allows for codebook development, tailoring it to the subject's needs in the future. Topics include: feasibility, acceptability; missing features; telehealth's impact (including sound/video quality); Amulet's usability and perceived barriers to use; complexity and flaws; strategies for improving compliance; feedback. Quantitative data will be measured using the 15-item, 5-point scale (*Telemedicine satisfaction questionnaire*⁶²).

Data Analysis: The analysis of Aim 1 is primarily descriptive. Data will be analyzed as follows:

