- Qualitative Data: Thematic analysis⁷¹⁻⁷³ will be conducted by two researchers who will independently read transcripts, and conduct open coding⁷⁴. This enhances research rigor by allowing for different viewpoints⁷⁵. Through data immersion, focused coding using themes identified during open coding permits defined analyses⁷⁴. Codes will be derived *a priori* from interviews, and inductively derived from qualitative data, after which, the query tool will retrieve text by code, reviewed for content, relevance, and prevalence of themes.
- Statistical Analyses: Descriptive statistics (means, medians, proportions, 95% confidence intervals [CI]) will be computed for feasibility/acceptability. Telemedicine satisfaction will be assessed only at 12 week follow-up
- Sample Size Considerations: For the pilot, we estimation the proportion of patients attending and completing 10 of 12 scheduled sessions. If this proportion is 80%, then the half width of the expected 95%CI based on 30 enrolled patients is 14.3%, based on a normal approximation for binomial data.

Aim 2: Assess the potential effectiveness of an eHealth-delivered health coaching obesity intervention in improving weight, physical function and self-reported health in adults with obesity.

Objective & Subjective Participant-Level Outcomes:

- Weight & BMI: Weight will be measured using a Seca 770 analyzer (in clinic) and by the Omron HBF-514 (at home remotely). Target weight loss is defined by >5% of weight. BMI is calculated by Quetelet's formula⁷⁶.
- Physical function: *6-Minute Walk (6MWT)*⁶³ is a cardiovascular fitness surrogate measuring distance (normal 400-700m)^{77,78} related to function. A clinically important difference is 50-55m⁷⁹.
- Diet/Exercise: The Rapid Eating Assessment for Participants (REAPS)⁶⁴ is a 16 item survey (score 13-39) of diet habits. The 7-item international physical activity questionnaire (IPAQ) measures health-related activity⁶⁵.
- Subjective Health: The 10-question, non-proprietary *Patient Reported Outcomes Measurement Information Systems General Health-10 (PROMIS)*⁶⁶ captures physical, mental and social aspects of quality of life.
- Readiness to Change: The University of Rhode Island Change Assessment⁶⁷ is a 12 item questionnaire assessing one's stages of change based on contemplation, action, maintenance and pre-contemplation.

Data Analysis: Aim 2 will evaluate potential effectiveness of the intervention on patient outcomes:

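### The telemedicine satisfaction questionnaire has one late timepoint and no assessment at withdrawal, so its summary may overstate satisfaction

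*Combined protocol and SAP*

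**What the plan says.** H1b in the Specific Aims states that the intervention is "acceptable in rural adults seeking treatment for obesity (using semi-structured interviews and Yip's Telemedicine survey"). Acceptability thus has two sources, one qualitative and one quantitative, and no numerical threshold.

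On the quantitative source, the Acceptability paragraph of Aim 1 says "Quantitative data will be measured using the 15-item, 5-point scale". The Aim 1 Statistical Analyses bullet promises descriptive statistics with 95% confidence intervals and adds: "Telemedicine satisfaction will be assessed only at 12 week follow-up".

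On the interviews, the same paragraph says "The RA will conduct, record, and transcribe each 30min interview". It gives no timing and does not say whether patients who withdraw are interviewed.

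Table 1 lists the "Yip Telemedicine questionnaire" with a single tick. In the extracted text that tick, like the interview's, appears to stand under timepoint 2 rather than 3. The column may have shifted in extraction.

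On numbers, the Feasibility paragraph says "Enrollment success will be defined as 30 patients" and "Adequate retention is defined as a dropout rate of <20" per cent. It also provides for collecting reasons for dropout and computes session completion and assessment completion over all enrolled patients. No analysis set or missing-data rule is given for the questionnaire. The only missing-data statement concerns the Aim 2 mixed models.

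**The concern.** A patient who stops after a few weeks has already used the video coaching and the wrist device and could rate them, but the plan creates no occasion to ask. If some patients leave because they dislike the intervention, the lowest ratings are the ones most likely to be missing. The gap between respondents and all enrolled patients would then widen as acceptability falls.

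The pilot is meant to inform a larger randomised trial. With no threshold for H1b, the descriptive summary carries the quantitative part of the claim, so readers need to know whom it describes. A logged reason for dropout is useful, but it is not a questionnaire score and does not enter the summary.

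**Working it through.** **Inputs from the plan.** Enrolled: 30. Dropout regarded as adequate: below 20%. Since 20% of 30 is 6, at most 5 patients can leave with the criterion still met, which leaves 25. Scale: 15 items, 5 points.

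**Inputs assumed.** The documents give no expected score, no expected proportion satisfied and no cutoff for being satisfied. The values below are illustrations, and they suppose that everyone still present at 12 weeks answers.

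**The plan's own Aim 1 figure.** The only precision figure is a half-width of 14.3% for an 80% session-completion proportion in 30 patients: 1.96 × √(0.8 × 0.2 / 30) = 0.143. It reproduces. With 25 respondents the same formula gives 1.96 × √(0.8 × 0.2 / 25) = 0.157. Losing five respondents therefore costs little precision. The issue is selection, which a confidence interval computed from respondents does not reflect.

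**Proportion satisfied, five leavers.** Suppose 23 of 25 completers are satisfied, 23/25 = 92%.
- Worst case, no leaver satisfied: 23/30 = 76.7%.
- Best case, all leavers satisfied: (23 + 5)/30 = 93.3%.

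The completer figure could be too high by up to 15.3 percentage points (92.0 − 76.7) or too low by 1.3 (93.3 − 92.0).

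**Mean score.** With d leavers, overstatement = (d/30) × (completer mean − leaver mean). For a completer mean of 4.0:

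| Leavers | Leavers score 3 | Leavers score 2 | Leavers score 1 | Leavers score 4 |
|---|---|---|---|---|
| 1 | 0.03 | 0.07 | 0.10 | 0 |
| 3 | 0.10 | 0.20 | 0.30 | 0 |
| 5 | 0.17 | 0.33 | 0.50 | 0 |

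For example, 5/30 × (4.0 − 1) = 0.50. If leavers scored above completers, the sign would reverse.

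**Timing.** The design is a 12-week pilot with monthly assessments, so timepoint 3 is naturally read as week 12. A tick under timepoint 2 would not agree with the Aim 1 text. If that tick is real, patients who left after timepoint 2 would already have been assessed, but earlier leavers would still be missed. The concern survives either reading.

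**The case against.** The strongest reply is that the sentence fixes a timepoint and does not define an analysis set. Satisfaction cannot be rated before exposure, so the natural sense is that there is no baseline measurement; Aim 3 words its staff measures similarly. The plan also counts session completion and assessment completion separately, so a patient who stops sessions might still be approached at week 12. This stands. A reader might infer that leavers are deliberately excluded, but the documents are silent on whether they are approached.

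A reader might also infer that acceptability as a whole is measured only in completers. The documents do not support that: the 12-week sentence covers the questionnaire, and the interview text neither includes nor excludes people who withdraw. Interviews yield themes, however, and cannot supply the missing scores.

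The plan has some protection already. Reasons for dropout are collected, and early leaving counts against the completion rate, so readers will see how many left. Because H1b has no threshold, no pass/fail decision is shown to change. These points limit the consequence but do not fill the gap in the questionnaire summary.

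Finally, dropout can have causes unrelated to satisfaction, such as illness, relocation or technical failure. That is why the bias is possible and not established.

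**Conclusion.** The point holds in a limited form. The only quantitative acceptability measure has one late assessment and no provision at withdrawal, so its summary may overstate satisfaction. With the five leavers that the retention criterion allows, the illustrations give an all-enrolled proportion of 77% to 93% against 92% in completers, or an overstatement of 0.17 to 0.50 points if leavers score 3 down to 1 against a completer mean of 4.0. These sizes rest on assumed scores and on the link between leaving and dissatisfaction, which is plausible but undocumented. Below 20% is a success criterion and not a cap, so more than five could leave.

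Two stronger conclusions do not follow. One is that H1b is biased upward: the bounds around 92% include no bias and a slight understatement. The other is that a primary outcome is compromised: Aim 1 is nowhere designated primary, and the outcomes so labelled are percentage weight loss and BMI change under Aim 2.

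For a descriptive single-arm pilot this is a modest weakness, but it is cheap to repair and worth repairing.

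**What to change.** 1. In the Aim 1 Statistical Analyses, change the timing of the questionnaire to: *at 12 weeks or at withdrawal, whichever is first*. Use the same 15-item self-administered form, and offer the interview to those willing.
2. Report the number of respondents over the number enrolled beside the satisfaction summary.
3. If a proportion satisfied is reported, define the cutoff in advance and add best- and worst-case bounds over all enrolled patients. Label them as a sensitivity display. Counting every non-respondent as not satisfied is only the worst case and should not be the main estimate; it also cannot be applied directly to the planned means and medians.
4. Reconcile the Table 1 tick for both acceptability rows with the Aim 1 text.

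The cost is about five or six extra self-completed forms, using the research assistant and web/tablet data capture already planned, and one more table line. Once a cutoff is set, the bounds need no new data. Two limits remain: some who withdraw will not answer, and ratings given at withdrawal reflect shorter exposure, so they should be identifiable in the report.

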Study Population/Recruitment: The DH-WWC evaluated 315 new patients in 2016 (current waitlist ~ 3 mo.). As research director, the PI has access to subjects. To meet a target of n=30, $\sim 10\%$ of subjects would need to be enrolled. Staff will receive an overview at a weekly meeting. A research assistant (RA) will screen booked subjects by EHR review and identify eligible subjects. At the visit, the RA will proceed with a 2-way discussion focusing on the study goals, answering queries, providing contact details, and obtaining consent and baseline measurements. A Callahan score⁵⁸ ≥ 4 and no EHR diagnosis of dementia will assure competence for consent.

Retention: To minimize dropouts, we will provide feedback (ie: weight), frequent contacts, study incentives for assessments, and assertive outreach with the primary care provider (to engage partnerships). We anticipate that the duration of the pilot and patient motivation will lead to favorable retention.

Baseline Measures: We will review EHR records for: age, race, co-morbidity, education, medications, and habits. We will ask about social support^{59,60} at baseline.

Intervention Description: The pilot comprises of five components listed below which provide access to specialty obesity care to rural obese adults, and enhance it with technology (telehealth and remote monitoring):

a) **Team-based care:** As in other US-based specialty obesity centers, the DH-WWC is an interdisciplinary, team-based, specialty clinic overseeing each patient's care: a physician or associate provider formulates a medical plan and counsels on obesity's adverse effects; a nurse assists in triaging medical concerns and manages drug therapy; a psychologist evaluates the patient for barriers to weight-loss such as untreated or underdiagnosed mental health disorders; and a dietitian counsels the patient on nutrition/energy needs for achieving weight loss through nutritional therapy. The health coach is supervised by the clinician.

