- Statistical Analyses: We will assess % weight loss and BMI change (primary outcomes), and change in the 6MWT, REAP-S, IPAQ, PROMIS and URICA (secondary outcomes). Linear/non-linear mixed effects models will evaluate weight, BMI and URICA change over time. To account for repeated measures and variation in trajectory over time, models will include random individual-level intercepts and time trends. A significant coefficient for the mean trend over time will indicate changes in outcomes. All data will be included as the models are robust to data missing at random under the assumptions of a linear mixed model. Paired t-tests will assess the change between baseline and follow-up in 6MWT, REAP-S, IPAQ and PROMIS.
- Sample Size Considerations: This pilot study intends to help develop future studies to evaluate recruitment, feasibility, acceptability and outcomes. Given the longitudinal nature of the data, a key parameter driving the future design is the intraclass correlation coefficient (ICC), a measure of dependence between observations taken on the same person. With 30 participants and a mean of 10 observations/person, we should be able to distinguish between a fairly low ICC of 0.15 versus an alternative of 0.34, based on a one-sample hypothesis test with a significance level of 0.05 and a power of 90%⁸⁰. For the primary outcome of % weight loss, using

a SD of 10.1%, the 95% CI would have half width of 3.6% based on our sample of 30, assuming a normal distribution.

Aim 3: Ascertain the extent to which the intervention works within an existing specialty obesity clinic on implementation outcomes such as workflow adoption, organizational change and compatibility.

Objective and Subjective Adoption, Implementation and Compatibility-Level Outcomes:

- Adoption Domain: *Workflow Adoption*: Questions using semi-structured interviews (methods per Aim 1) from the staff's experience with the intervention (whether it enhances/interferes with workflow; sustainability; technical or other difficulties in delivering care) will be explored. *Staff Adoption*: Haug's 12-item *Measure of Evidence-Based Practice Adoption*⁶⁸ assesses stage of change, experience, attitudes, organization barriers and strategies to support evidence-based practices (1-5 point scale - strongly disagree to agree).

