- Implementation Level: *Organizational Change*: General Organizational Index (GOI)⁶⁹ is an interview of 11 domains with a 5-point rating of: program philosophy, commitment, client eligibility and identification, health promotion plan and its treatment, training, process and outcome monitoring, assessment, quality assurance, choice supervision, & penetration. It has reliable inter-rater agreement and internal consistency.
- Compatibility: *Patient Perception of Value*: Two questions will assess *Willingness to Pay (WTP)*⁷⁰ – whether they would pay for telemedicine delivery of the intervention in lieu of in-person travel time or cost.

Data Analysis: We will use mixed-methods to analyze data from Aim 3 as follows:

- Qualitative Data: Interview data will be managed and analyzed using *Dedoose* as described in Aim 1.
- Statistical Analyses: Descriptive statistics (means, medians, 95% CI) for adoption, organizational change will be assessed at follow-up only. Changes in WTP will be estimated using a paired 2-sample t-test.
- Sample Size Considerations: For changes from baseline on WTP, there will be 80% power to detect large differences in change from 0.32 to 0.28 times a SD assuming a range of within-person correlations (0.2-0.4).

Data Management: Our team is experienced in pilot delivery, data management/acquisition, and validation procedures including: a) health coach training; b) continuous feedback; and c) final data editing. The PI and co-l's will meet staff regularly, supervise and identify quality control issues early to address them promptly. Non-HER entered measures will be collected by the RA using REDCap⁸¹, a secure web/tablet based data collection tool. The Analytics Institute manages a DH-WWC patient registry who will facilitate data extraction. Interviews will be recorded in duplicate using a digital tape recorder. Records will be kept in a locked cabinet. Identifiers will be assigned at enrollment and kept behind the D-H firewall, with a password protected linked file. Data will be exported to *Dedoose* and *R* for analysis with complete labeling intact (variables, labels, missing values)

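### Does naming a clinic scale and a home scale for weight, without assigning either to a timepoint, put the 12-week weight outcome at risk?

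*Combined protocol and SAP*

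**What the plan says.** The Weight & BMI item under Aim 2 (Objective & Subjective Participant-Level Outcomes) reads: "Weight will be measured using a Seca 770 analyzer (in clinic) and by the Omron HBF-514 (at home remotely"). Neither scale is mentioned anywhere else. The same item sets the target at a loss of more than 5% of weight.

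Four other places bear on which scale is used when:

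- Table 1, Aim 2: the row "Weight/body mass index" is administered by clinical staff at timepoints 0, 1, 2 and 3. The row "6 minute walk test (6MWT") is administered by clinical staff at 0 and 3. The table has a separate code for self-administered measures, and weight does not carry it.
- Study Population/Recruitment: the research assistant's tasks at the visit include "obtaining consent and baseline measurements".
- Aim 2, Statistical Analyses: "Linear/non-linear mixed effects models will evaluate weight, BMI and URICA change over time", and "models will include random individual-level intercepts and time trends". On missing data, "All data will be included as the models are robust to data missing at random". No device term is mentioned.
- Data Management: "Non-HER entered measures will be collected by the RA using REDCap". Home weights and a device field are not mentioned.

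**The concern.** % weight loss and BMI change are the primary outcomes of Aim 2, and both are computed from weight. If baseline came from one scale and week 12 from the other, any systematic difference between scales would be added in full to every participant's change, and no control group would cancel it. Even with clinic weights at both ends, home readings fall after the clinic baseline. If they were pooled in a trend model without a device term, part of the offset could tilt the slope. If the device behind each reading were not recorded, the analysis could not be adjusted later. At stake is a distorted mean change, read against a 5% target.

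**Working it through.** **Plan's own figure.** Aim 2 gives SD 10.1%, n = 30 and a half width of 3.6% for % weight loss. Check: 1.96 × 10.1 / √30 = 3.61, which agrees. It is the yardstick below.

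**Which scale at which end.** The Weight & BMI item ties device to setting: Seca in clinic, Omron at home. Baseline is measured at the visit. At month 3 clinical staff administer both weight and the walk test. Read together, these put the Seca at both ends. A constant offset then cancels in the simple change, so its share is 0. BMI change behaves the same way, since height is fixed.

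**How much of an offset a pooled linear trend would carry.** Let d = 1 for a home reading and 0 for a clinic reading, with t in weeks. The share of a constant home offset that enters the 12-week change is

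share = 12 × Σ(t − t̄)d / Σ(t − t̄)².

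The document gives no home-weighing schedule, so these are illustrations:

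| Clinic weeks | Home weeks | Calculation | Share |
|---|---|---|---|
| 0, 12 | 4, 8 | 12 × 0 / 80 | 0 |
| 0, 12 | 1–11 | symmetric about week 6 | 0 |
| 0, 12 | 1–12 | 12 × 0.857 / 215.4 | 0.048 |
| 0, 4, 8, 12 | 1–12 | 12 × 1.5 / 223.75 | 0.080 |
| 0, 12 | 4, 8, 12 | 12 × 2.4 / 108.8 | 0.265 |
| 0, 4, 8, 12 | 1–8 | 12 × (−4) / 128 | −0.375 |
| 0 only | 1–12 | 12 × 6 / 182 | 0.396 |
| 0 only | 4, 8, 12 | 12 × 6 / 80 | 0.900 |

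Generalised least squares with a random intercept and slope gave the same shares on the schedules checked. With clinic weights at weeks 0 and 12 and eight home readings placed anywhere in weeks 1–11 (165 placements), the share runs from −0.245 to +0.245, with median absolute value 0.056. The extremes need every participant to weigh only early or only late. If timing varies at random across 30 people, the mean share is 0 with standard error 0.015.

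**In percentage points.** Assume an offset of 0.5 to 2 kg at 100 kg, that is 0.5 to 2.0 points; the document gives no figure.

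- Clinic at both ends, simple change: 0.
- Clinic at both ends, weekly home weights pooled: at most 0.080 × 2.0 = 0.16, about 4% of the 3.6-point half width (0.16 / 3.6).
- Home weighing that stops at week 8 in everyone: 0.375 × 0.5 to 0.375 × 2.0, or 0.19 to 0.75 in size.
- Week-12 weight taken at home, linear trend: 0.396 × 0.5 to 0.900 × 2.0, or 0.2 to 1.8.
- Week-12 weight taken at home, simple change: 0.5 to 2.0.

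**Would a device term help?** With clinic weights at weeks 0 and 12 and home weights at 4 and 8, d = t(12 − t)/32 exactly: 0 at weeks 0 and 12, and 1 at weeks 4 and 8. The device indicator is then a quadratic in time, so a device effect and a quadratic trend cannot both be fitted. On that schedule the share is 0 without the term, under a linear or a quadratic fit, so requiring it would rule out a curved trend for no gain.

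**The case for a change.** The strongest case for a change is that the reading above is inferred, not written. Table 1 applies the same clinical-staff code at months 1 and 2, although coaching is by video. The Omron is listed among outcome measures, not as an intervention component. The Aim 2 sample-size paragraph assumes a mean of 10 observations per person while Table 1 schedules 4 weights, so the plan seems to expect readings from elsewhere. Nothing forbids a home weight standing in for a missed month-3 visit. One sentence would settle all this.

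Some of it stands. The scale is not assigned to timepoints, and a substituted home weight would carry the full offset for that person. The Feasibility paragraph treats dropout below 20% as adequate; if home weights replaced as many as 20% of final weights, the mean simple change would move by at most 0.2 × 2.0 = 0.4 points under the same assumed offset. The 10 observations are not said to be weights or home readings, and the ICC calculation does not depend on which scale is used. The inclusion of all data is a statement about missing values, not a rule to pool devices. Nor does the absence of a named device field show that the source would be lost: Data Management describes separate routes for record-based and other measures, and export with labels intact.

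**Conclusion.** The plan leaves a detail unstated, but no rule or number in it is shown to give a wrong result. On its most natural reading the primary simple change uses the clinic scale at both ends and carries none of a constant scale offset. A linear trend pooling regular weekly home weights would carry 0 to 8%, at most 0.16 percentage points for an assumed 2 kg offset at 100 kg.

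A material bias would need all of the following: home readings pooled in the primary model; a systematic offset, for which the document gives no size; the same offset across participants' home scales, since independent offsets would largely average out; and either a home reading at week 12 or lopsided timing shared by nearly everyone. An analyst with clinic weights at baseline and month 3 would use them and treat home readings as supportive. This is a gap that competent analysts fill sensibly in a 30-person pilot, and a compulsory device term would gain nothing on the symmetric schedule. The conclusion rests on the month-3 weight being taken in clinic, which Table 1 implies but does not state.
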